In either case, the details of the study its risks and potential benefits will be explained by an investigator, and the parents are allowed to make an informed choice as to whether or not they decide to participate. If patient is transported the parents will be supplied with a copy of the consent form by the transport team and then contacted directly by an Investigator or when they arrive to our NICU.

- Provide the consent form in person, give prospective subject sufficient time to review the consent form and discuss with friends/family.
- Consent forms will also be given to the parents by the neonatology transport team and contacted directly by an Investigator.

8) Procedures Involved

This is a randomized double blind placebo controlled trial of newborns with neonatal encephalopathy undergoing our standard clinical protocol of whole body cooling. We will approach the parents of eligible infants, describe the study to them, and ask if they want their baby to participate in the study. Infants will be randomized by UCDMC pharmacy to receive cooling with placebo (control arm, n=21) or cooling with topiramate (study arm, n=21). At UC Davis, whole body cooling is a standard treatment for all infants with neonatal encephalopathy.

Active cooling will begin as soon as an infant is admitted to our NICU, using whole body cooling with a goal core temperature of 33.5 degrees Celsius and will be continued for 72 hours. Subject temperature will be monitored continuously using a rectal temperature probe and skin integrity is monitored closely with frequent turning of the

PROTOCOL TITLE: Topiramate for infants receiving whole body cooling in neonatal encephalopathy

infant. After 72h of cooling, babies are slowly rewarming back to normal body temperature over a period of 12h.

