Infants assigned to the topiramate group will receive 5mg/kg of topiramate daily enterally for a total of 5 doses. This is the minimum therapeutic dose of topiramate for infants. The first dose will be administered on the day of enrollment and will continue through and after rewarming. The duration of drug administration was chosen to encompass the cooling period as well as a brief period after rewarming is complete as this is a period where some infants develop seizures and display more signs of neurological damage. The control group will receive a placebo instead of topiramate. Pharmacy will prepare and send to NICU the placebo or study drug solutions in a way to be similar in appearance and volume. Initiation of cooling will not be delayed, but families will be approached for consent as soon as possible after cooling has started.

The cooling protocol includes a range of laboratory evaluations which will be carried out irrespective of whether the patient is enrolled in the study. These include: complete blood count, PTT/INR, DIC panel, complete metabolic panel, ammonia, lactate, troponin-I, CK panel, blood gas, and urinalysis at the initiation of cooling and then every 24h until rewarming is complete (unless the Attending Neonatologist decides that more frequent or less reassessments are needed clinically). Blood gases, blood glucose and ionized calcium levels are measured at the initiation of cooling and then every 6h until rewarming is complete. Once labs have normalized per the discretion of the covering Attending some of these labs may be discontinued. These lab values will provide important data of the severity of each infant's hypoxic-ischemic insult and for patient safety monitoring including information on liver function, kidney function, ammonia toxicity, metabolic status, and acidosis. Enrollment in the study will not change the frequency of these assessments.

A single channel EEG recording (an amplitude EEG, aEEG) or continuous video EEG is recorded continuously on all patients until rewarming is complete. This method measures the degree of encephalopathy and detects seizures.

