The Pediatric Neurology service is by protocol consulted on all cooling patients. They will evaluate the infant and determine a neonatal encephalopathy score daily under the supervision of our Pediatric Neurologists. The presence of clinical seizures will be noted based on review of the bedside aEEG or cEEG. The aEEG/cEEG data will be reviewed in 3 hour increments and document the time when the voltages on the aEEG/cEEG first return to normal. The aEEG/cEEG is used throughout the cooling phase and is generally discontinued after rewarming is completed but may be continued longer for abnormal tracings such as seizures at the discretion of the Neonatology Attending. In addition, the Attending Pediatric Neurologist will assess quality of movements, posture, reflexes, and muscular tone, each infant's neurologic status will be categorized as normal (completely normal neurologic status), unspecific signs (eg, asymmetric muscle tone or reflexes) or abnormal with lack of reflexes and bilateral muscular hypotonia or hypertonia.

Additional tests in infants enrolled in this research study include: serum UCHL1 and urine levels of S100 β , both will be measured at enrollment, at the start of rewarming, and at one-week of life. Topiramate trough drug levels will be collected 24 hours after the first, third, and fifth doses. The drug levels will be run by the UCDMC laboratory. These

PROTOCOL TITLE: Topiramate for infants receiving whole body cooling in neonatal encephalopathy

are the only additional laboratory assessment that study infants will receive as a result of taking part in the study.

All infants on the cooling protocol, irrespective of the research study, will have an MRI with spectroscopy on day 5-7 of life. For this study, these images will be read by a single radiologist, our collaborator [name] of Neuroradiology. The reporting of MRI and MRS results will be standardized in conjunction with [name] to create a more consistent scoring method.

Following discharge, each infant will receive long-term developmental follow-up through the MIND clinic our High Risk Infant follow-up clinic. Infants will be seen at approximately 9, 18, and 27 months. The infants will have standardized Bayley Scale of Infant Development (BSID) III neurodevelopmental screening at these clinic follow-ups supervised by [name].

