Meier analysis. The effect of treatment on S100 β levels in the urine or UHCL1 in the blood and on other markers of tissue injury will be compared using ANOVA (for outcomes measured once) and by repeated measures ANOVA for those measured on more than one occasion, at predetermined times.

Effect of treatment assignment of development assessments will be assessed individually at the 9m, 18m and 27m examinations.

All tests will be considered significant at $p<0.05$. Where necessary, Tukey-Kramer's test will be used to account for multiple comparisons

Data Specimen/Management

Data specimens will be stored in the NICU and numerically coded, only those who are involved with this study will have access to the specimens. The specimens will only be stored for the duration of the study and thereafter discarded.

10) Data and/or Specimen Banking

There is no plan for specimen or tissue banking in the future.

11) Provisions to Monitor the Data to Ensure the Safety of Subjects

To monitor the safety of each newborn we will track the following variables closely during the intervention: blood gases, blood pressure (hypotensive episodes and required interventions), evidence of seizure activity, and serum topiramate levels. This study is only applicable to newborns with neonatal encephalopathy admitted to the NICU at UC Davis for cooling therapy. Neonatal encephalopathy is a life threatening disease with 30% chance of death and 64% chance of seizures during the neonatal period. These patients receive 24 hours daily continuous extremely close physiological and biochemical monitoring based on their underlying disease state.

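### Scheduled blood gases and chemistry stop when rewarming ends (about 84 h), but dosing continues: at 24 h spacing dose 5 falls at 96 h or later, with only a drug trough tied to it

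*Combined protocol and SAP*

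**What the plan says.** **Cooling (Section 8).** "After 72h of cooling, babies are slowly rewarming back to normal body temperature over a period of 12h"

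**Dosing (Section 8).** Infants in the active arm "will receive 5mg/kg of topiramate daily enterally for a total of 5 doses", and the control arm receives placebo instead. Dose 1 is given on the enrollment day. The stated reason for the length of the course is to span cooling and a short time beyond rewarming. Families are approached once cooling is under way.

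**Routine laboratory tests (Section 8).** The panel, which includes a complete metabolic panel and ammonia, is done "at the initiation of cooling and then every 24h until rewarming is complete". Blood gases, glucose and ionized calcium are done every 6 h to the same end point. The attending may order the panel more or less often, and may drop some tests once values are normal. Section 8 adds: "Enrollment in the study will not change the frequency of these assessments".

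**Study-specific tests (Section 8).** These are serum UCHL1, urine S100β and drug levels: "Topiramate trough drug levels will be collected 24 hours after the first, third, and fifth doses". The section says that nothing else is added.

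**Safety monitoring (Sections 11 and 13).** Section 11 states: "we will track the following variables closely during the intervention: blood gases", followed by blood pressure, seizure activity and topiramate levels. Section 13 discusses metabolic acidosis, raised creatinine and BUN, and low potassium. For these it points to gas monitoring in cooled infants and to standard-of-care renal and potassium monitoring. It also counts bicarbonate and bronchodilator doses, both on study treatment and over the whole hospital stay, for the DSMC.

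**The concern.** The dosing window was extended past rewarming on purpose, but the laboratory window was not. Once rewarming ends, whether an infant has a gas, creatinine, BUN or potassium result depends on a clinician deciding to order it.

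Two things follow. First, an investigator who follows Section 8 exactly will not deliver what Section 11 says about gases. Second, late laboratory values will come from infants whom clinicians chose to sample, so any later tabulation of them by arm would be incomplete and selective.

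This matters in a trial of 21 infants per arm. Section 13 cites raised creatinine in 5% on topiramate against 0% on placebo, and low potassium in 7% against 0%. Purely as an illustration, 21 × 0.05 ≈ 1 infant and 21 × 0.07 ≈ 1.5 infants. Whether one infant happens to be sampled late could change the picture.

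**Working it through.** The documents state neither 84 h nor 96 h, so there is no figure of the plan's own to reproduce. Time zero is the start of active cooling.

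**1. End of scheduled tests.** 72 h cooling + 12 h rewarming = 84 h.
- Gases every 6 h: 0, 6, …, 84 h. The last is at 84 h.
- Panel every 24 h: 0, 24, 48, 72 h. The next slot, 96 h, is after rewarming, so the last is at 72 h.

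**2. Dose times.** Let *d* be the delay from the start of cooling to dose 1. Consent is sought after cooling has begun and pharmacy sends the study drug to the NICU, where active cooling starts on admission, so *d* is not negative. Its size is not stated; I assume 0 to 24 h. At 24 h spacing, dose *k* is at *d* + 24(*k* − 1), dose 5 is at *d* + 96, and the dosing interval ends, with the trough, at *d* + 120.

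**3. Share of the 120 h dosing interval after the last scheduled test.**
- After the last gas: (*d* + 120 − 84)/120 = (*d* + 36)/120
- After the last panel: (*d* + 120 − 72)/120 = (*d* + 48)/120

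| *d* (assumed) | Dose 5 at | Last gas to dose 5 | Share after last gas | Share after last panel |
|---|---|---|---|---|
| 0 h | 96 h | 12 h | 36/120 = 30% | 48/120 = 40% |
| 6 h | 102 h | 18 h | 42/120 = 35% | 54/120 = 45% |
| 24 h | 120 h | 36 h | 60/120 = 50% | 72/120 = 60% |

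Dose 4, at 72 + *d*, follows the last panel whenever *d* > 0, and follows the last gas when *d* > 12 h.

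**4. Is 24 h spacing the right reading?** The text says only that dosing is daily. Section 8 places trough levels 24 h after doses 1, 3 and 5. A level 24 h after dose 1 is not a trough if dose 2 has already been given, so the trough times support 24 h spacing.

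The alternative is fixed-clock dosing on successive calendar days. If cooling starts at clock hour *c* and later doses are given at hour *H*, dose 5 is at 96 + *H* − *c*.
- Cooling at 22:00, doses at 09:00: 96 + 9 − 22 = 83 h
- Cooling at 20:00, doses at 06:00: 96 + 6 − 20 = 82 h

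Dose 5 then just precedes 84 h, but 83 + 24 − 84 = 23 h and 82 + 24 − 84 = 22 h of its interval still follow it. Since *H* − *c* is always above −24, dose 5 is always later than 72 h. Its interval therefore ends after 96 h, and more than 96 − 84 = 12 h of it is uncovered on any calendar-day schedule.

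**5. What still covers dose 5.**

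| Item | Position after rewarming |
|---|---|
| Blood gases; creatinine, BUN, potassium, ammonia | Not scheduled |
| Topiramate level | Scheduled 24 h after dose 5 |
| Blood pressure, clinical observation | No stop stated |
| Bicarbonate and bronchodilator counts | Continue through hospitalization |
| UCHL1, S100β at one week | Scheduled, but injury markers not tied to dosing |

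**The case against.** The best defense is that monitoring does not end with the cooling schedule. Section 11 describes round-the-clock physiological and biochemical observation. Section 13 calls creatinine, BUN and potassium monitoring standard of care and gives no end time. Its reassurance on acidosis is tied to cooled infants and to a deep-hypothermia subgroup, so the gas schedule arguably meets that sentence on its own terms. The DSMC receives bicarbonate and bronchodilator counts by coded arm, with a P<0.1 trigger, and these reach beyond dose 5. No between-arm analysis of gases or chemistry is specified as a safety endpoint.

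Much of this stands. A reader might infer that the fifth dose and its whole interval, in all 42 infants, always fall outside the monitoring that the risk section relies on. The documents do not support that. The drug level, blood pressure and clinical observation are also named safeguards. Exact 24 h spacing and on-time rewarming are not written down. Section 8 lists what is scheduled and does not say that testing ceases. Nor are the earlier tests guaranteed, since the attending may reduce or stop some of them; that can only widen the gap.

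The defense does not remove the mismatch. General observation and standard of care carry no schedule, and the one schedule the protocol gives stops at rewarming. Bicarbonate is given when acidosis is found, so after rewarming that count depends on who was sampled. Section 11 names blood gases specifically and ties them to the intervention, not to cooling.

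**Conclusion.** The mismatch is real and limited to scheduled blood gases and chemistry. Gases end at about 84 h and the 24-hourly panel at 72 h, while dose 5 falls at 96 h or later at 24 h spacing. The only study laboratory test tied to dose 5 is the drug trough. Between 30% and 50% of the dosing interval has no scheduled gas.

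This rests on 24 h spacing, rewarming completed on time, and an assumed delay of 0 to 24 h before dose 1. On a calendar-day reading the gap shrinks but stays above about 12 h of the dose 5 interval. These figures describe the schedule, not the tests clinicians would actually order.

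**What to change.** Reconcile Sections 8, 11 and 13 so that the stated safety-laboratory window and the dosing window agree in both arms, and state the dosing interval in hours so that the two can be compared.

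One low-cost way is to record blood gas, creatinine, BUN and potassium as study safety data from the draw already planned 24 h after the fifth dose. The Section 8 sentence limiting the additional laboratory tests would need amending, and it should say that the draw is taken in both arms. This yields one common post-dose-5 value per infant, free of clinician selection. It leaves the hours between the end of rewarming and that draw without a scheduled gas, so the Section 11 wording should also be brought into line with whatever schedule is adopted.

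The cost is slightly more blood volume and a protocol and consent wording change. The documents give no sample volumes, so calling this small is a judgment. The change concerns data collection only: it proposes no dose, stopping or treatment rule, and how results are acted on stays with the clinical team.

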The BSID-III contains 3 domains: cognitive, language (receptive and expressive communication), and motor (fine and gross motor). The cognitive scale includes items that assess sensory perceptual development, exploration and manipulation, object relatedness, concept formation, memory, and other aspects of cognitive processing. To allow comparison of results from the 3 domains, a composite score is calculated for each domain (mean, 100). A composite score below -2 SD (<70) is considered a severe delay for all domains. A Pediatrician will assess the quality of movements, posture, reflexes, and muscular tone at each clinic visit. Each infant's neurologic status will be categorized as normal gait and walking, unspecific neurological signs (eg, asymmetric muscle tone or reflexes, muscular hypotonia), or abnormal with upper and/or lower extremities muscular hypertonia (signs of cerebral palsy (CP) present).

9) Data and/or Specimen Management and Confidentiality

Power Calculation

Our primary hypothesis is that topiramate will reduce the frequency of early seizures (i.e. before hospital discharge). From our current data, 64% of infants have seizures prior to hospital discharge; a sample size of 42 will have an 80% chance of detecting a reduction of seizure rate by 2/3 with a p-value of 0.05.

Statistical Methods

Our primary outcome is that seizures before hospital discharge will be significantly reduced in the topiramate group compared to the controls. This will be assessed by nominal logistic regression with the presence or absence of seizures as the nominal dependent variable, and treatment group (topiramate or control) as an independent variable. Other independent variables will include those that are unbalanced between the treatment groups at randomization, and factors that could affect the risk of seizures (these would include neonatal encephalopathy score at study entry, time to initiation of cooling (< or \geq 3h), gender etc).

The effect of treatment assignment on neonatal encephalopathy score (measured daily) will be assessed by repeated measures ANOVA with neonatal encephalopathy score as the dependent variable, time and treatment assignment as the independent variable, and addition independent variables included as appropriate (see above). Time to normalization of aEEG/cEEG in the two different groups will be assessed by Kaplan-

PROTOCOL TITLE: Topiramate for infants receiving whole body cooling in neonatal encephalopathy

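### The follow-up neurological scale has no level for an infant with a normal examination who is not yet walking, so its normal level carries little information at the 9-month visit

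*Combined protocol and SAP*

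**What the plan says.** All the follow-up wording is in Section 8 (Procedures Involved) of the combined protocol and SAP.

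- Visits: "Infants will be seen at approximately 9, 18, and 27 months".
- Examination: "A Pediatrician will assess the quality of movements, posture, reflexes, and muscular tone at each clinic visit".
- Classification, in the next sentence: "neurologic status will be categorized as normal gait and walking" for the first level, then a second level of unspecific signs, with asymmetric tone or reflexes and hypotonia as examples. The third level is "abnormal with upper and/or lower extremities muscular hypertonia (signs of cerebral palsy (CP) present".
- Bayley testing at the same visits: "The infants will have standardized Bayley Scale of Infant Development (BSID) III neurodevelopmental screening at these clinic follow-ups".

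Section 8 also has an inpatient neurological scale whose normal level names no motor milestone: "categorized as normal (completely normal neurologic status), unspecific signs (eg, asymmetric muscle tone or reflexes".

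Section 2 lists developmental outcomes at the three ages among the secondary objectives. Section 9 (Statistical Methods) adds: "Effect of treatment assignment of development assessments will be assessed individually at the 9m, 18m and 27m examinations". It does not name the neurological category as an analysed outcome and gives no test for it.

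**The concern.** The examination has four items: movement quality, posture, reflexes and tone. Gait is not one of them, yet the only normal level of the scale is defined by gait and walking, with no allowance for age. At 18 and 27 months that may be workable. At 9 months, an infant who is normal on all four items but does not yet walk has no place on the scale.

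The examiner can leave the infant unclassified, record unspecific signs that are not there, or set the written definition aside. Nothing in the plan says which, and different examiners may choose differently. The infants affected are those with a normal examination, which is the group a neuroprotection trial hopes to enlarge. If the category is compared between arms at 9 months, a real difference in the proportion who are normal could be hidden.

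**Working it through.** **Plan's own figure.** The documents give no calculation for this scale. The only design calculation is the total of 42 infants for the seizure outcome, which does not enter here.

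**Step 1: does the scale apply at 9 months?** One visit is at about 9 months, the examination is done at each visit, and the classification sentence follows directly with no age limit or exemption. That is the natural reading, although the classification sentence does not itself name a visit.

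**Step 2: do the three levels cover every infant at 9 months?**

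| Infant | Normal level | Unspecific level | Abnormal level |
|---|---|---|---|
| Normal examination, walking | fits | no | no |
| Normal examination, not yet walking | no | no | no |
| Asymmetry or hypotonia | no | fits | no |
| Limb hypertonia, signs of CP | no | no | fits |

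The second row has no home. The last two rows do not depend on walking.

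**Step 3: what is recorded under each way of handling the second row?** Let p be the true proportion with a normal examination and w the share of those infants who walk at 9 months, the same in both arms. Neither is in the documents. For illustration, p = 0.50 and 0.75 (a 25-point difference), and w runs from 0 to 1.

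- Recorded as normal, under literal use: p × w. At w = 0.10 this is 5.0% vs 7.5%, or 21 × 0.05 = 1.05 vs 21 × 0.075 = 1.58 infants.
- Any sign, non-walkers left unclassified but kept in the denominator: 1 − p = 50% vs 25%. All 25 points remain.
- Any sign, unclassified infants dropped: (1 − p)/[(1 − p) + p × w]. At w = 0.50 this is 66.7% vs 40.0% (26.7 points). At w = 0.10 it is 90.9% vs 76.9% (14.0 points). At w = 0 it is 100% vs 100% (0 points).
- Any sign, non-walkers labelled unspecific: 1 − p × w. At w = 0.10 this is 95.0% vs 92.5% (2.5 points).
- Number rated abnormal: the same in every case.

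**Step 4: power on the normal level.** Two-sided Fisher exact test at 0.05, with 21 per arm all followed up. Type I error is computed with both arms at 0.50 × w.

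| w | Recorded normal | Power | Type I error |
|---|---|---|---|
| 1 | 50% vs 75% | 26% | 2.0% |
| 0.50 | 25% vs 37.5% | 7.8% | 2.3% |
| 0.25 | 12.5% vs 18.75% | 4.2% | 1.8% |
| 0.10 | 5% vs 7.5% | 0.7% | 0.2% |
| 0.05 | 2.5% vs 3.75% | 0.06% | 0.02% |
| 0 | 0% vs 0% | 0 | 0 |

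Information is lost as w falls, but no false difference between arms appears: type I error stays at or below 2.3% throughout. Comparing any sign with none, with all examined infants in the denominator, is the mirror image of the first row and keeps its 26%.

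**The case against.** A reader might infer that the 9-month comparison as a whole is invalid. The documents do not support that. BSID-III composites in three domains are obtained at the same visit and do not use the walking wording. Section 9 speaks of development assessments, and the Bayley is the most direct reading of that. A reader might also infer that the scale merely records early walking at 9 months. That is wrong for two of its three levels, and Step 3 shows the full difference can survive if non-walkers stay in the denominator and are not called unspecific. Nor does the wording favour an arm: allocation is randomized and double-blind, so the gap falls on both alike.

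Three further objections have weight. Use of the scale at 9 months follows from two adjacent sentences and is not stated outright, and Sections 13 and 14 mention a neurological examination only at 18 months. The illustration rests on assumed rates and on 21 infants per arm, whereas Section 11 cites a 30% chance of death. And even with perfect classification the illustrated power is only 26%, so this rating could never have carried much weight.

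These points limit the consequence but do not close the gap. No 9-month exemption appears, the levels still omit an expected type of infant, and nothing tells the examiner how to handle the omission. If the category is not meant to be analysed at 9 months, the plan should say so.

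**Conclusion.** The point holds for one secondary rating at one visit. On the natural reading of Section 8, an infant with a normal examination who is not yet walking at 9 months fits none of the three levels. The normal level is then uninformative at that visit, and so is the unspecific level if such infants are placed there.

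The conclusion needs only that some normally examined infants are not walking at 9 months, which is an assumption because the documents say nothing on it. The size of the loss depends on that share. Under the illustrative rates, power on the normal level ranges from 26% (all walking) to 0 (none walking).

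The effect is loss of information, not bias between arms. The 9-month BSID-III scores, the identification of infants with signs of CP, the 18- and 27-month ratings and the primary seizure outcome stand as they are.

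**What to change.** In Section 8, define normal at the 9-month visit as tone, posture, reflexes and movement quality all normal for age, with gait not required. This matches the inpatient scale, whose normal level needs no motor milestone. Keep the gait wording for 18 and 27 months.

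In Section 9, state whether the category is compared between arms at 9 months. If it is, use the new definition or a contrast that does not depend on walking (any sign vs none, or signs of CP vs none), with all examined infants in the denominator.

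For infants already seen at 9 months, re-derive the category only if the four items were recorded separately. The documents say they are assessed, not that each is recorded.

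The cost is one sentence in Section 8, one in Section 9 and a change to the follow-up form, with no extra visit, assessor or test. The downside is that the 9-month category is worded differently from the later ones, so changes in category between 9 and 18 months need care in interpretation.

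### The daily encephalopathy score has no stated last scoring day and no handling of deaths, so repeated measures ANOVA can lose the infants who die and let a survival difference appear as a score difference of opposite sign

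*Combined protocol and SAP*

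**What the plan says.** Section 8 (Procedures Involved) has the neurology service "determine a neonatal encephalopathy score daily". It gives no last day and no number of scores. Section 9 (Statistical Methods) says that the "neonatal encephalopathy score (measured daily) will be assessed by repeated measures ANOVA", with time and treatment as factors and "addition independent variables included as appropriate (see above". The list referred to is the covariate list for the seizure model: "these would include neonatal encephalopathy score at study entry", time to cooling, sex and others.

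Other measurements do have time limits. Section 8 fixes three sampling times for the injury markers, and the predetermined times mentioned in section 9 belong to those markers. The end of rewarming bounds the routine laboratory tests and, in general, the EEG. None of this bounds the encephalopathy score.

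Section 11 gives a "30% chance of death and 64% chance of seizures during the neonatal period". Survival to discharge goes to the safety committee, but nothing says how a death or a missing score enters the score analysis.

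**The concern.** Classical repeated measures ANOVA needs the same complete set of days for every infant. An infant who dies during scoring has an incomplete series and leaves the analysis, so the arms are compared among survivors, a group that treatment may itself change. If the sicker infants die, better survival on topiramate keeps more severe infants in that arm and makes its scores look worse. Poorer survival makes them look better. Without a fixed last day, the number of incomplete series is also left to a choice made after the data are seen.

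Separately, the cross-reference to the covariate list allows the entry score to be a covariate, while daily scoring allows the same value to be the first outcome. No drug effect can exist at entry, so averaging that value into the outcome dilutes the estimate.

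**Working it through.** **Inputs from the documents:** 21 infants per arm (section 8), 30% mortality (section 11), significance at 0.05 (section 9; two-sided assumed).

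**Assumptions not in the documents:** score SD 1, higher is worse; five scoring days including entry; within-infant correlation ρ of 0.6 or 0.7; correlation g between underlying severity and liability to die; topiramate mortality of 15%; a fraction f of deaths inside the scored period; no drug effect on any score.

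**1. Plan's own figure.** There is none for this analysis. The total of 42 is for seizures, 64% v 21.3%. The two-sided pooled formula gives 20 per arm, 40 in total, so it is reproduced closely, but it has no bearing here.

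**2. Infants lost.** At 30% mortality in both arms and f = 1, 42 × 0.70 = 29.4 complete series remain, and standard errors widen by √(42/29.4) = 1.20. At f = 0.5, 42 × 0.85 = 35.7 remain, and the factor is √(42/35.7) = 1.08.

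**3. Spurious difference.** If a proportion p with the highest liability dies, the mean liability of infants with complete series is −f·φ(z)/(1 − f·p), where φ(z) is the normal density at the cut-off: 0.3477 for p = 0.30 and 0.2332 for p = 0.15.

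- f = 1: control −0.3477/0.70 = −0.4967; topiramate −0.2332/0.85 = −0.2743; difference +0.222.
- f = 0.5: control −0.1738/0.85 = −0.2045; topiramate −0.1166/0.925 = −0.1260; difference +0.0785.

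Multiplying by g√ρ gives the difference in score (topiramate minus control, SD):

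| Deaths in scored period | g 0.5, ρ 0.7 | g 0.7, ρ 0.7 | g 0.9, ρ 0.7 | g 1, ρ 0.6 |
|---|---|---|---|---|
| All, formula | 0.093 | 0.130 | 0.167 | 0.172 |
| All, simulation | 0.091 | 0.133 | 0.169 | 0.18 |
| Half, formula | 0.033 | 0.046 | 0.059 | 0.061 |
| Half, simulation | 0.032 | 0.045 | 0.058 | not run |

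At g = 0, or with equal mortality, the result is zero. Reversing the rates (15% control, 30% topiramate) gives −0.13 SD at g = 0.7 with all deaths in the period.

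**4. False positives at 30% v 15%.** With all deaths in the period, simulated two-sided rejection is 7.2% (g = 0.7), 9.4% (g = 0.9) and 12.0% (g = 1, ρ = 0.6). With half in the period and g = 0.7 it is 5.0%.

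**5. Entry score.** Write the average over k days as [Y0 + (k − 1)P]/k, where Y0 is the entry score and P the post-entry mean. The averaged treatment effect is (k − 1)/k of the post-entry effect: 3/4 = 75% for k = 4 and 4/5 = 80% for k = 5. If Y0 is also a covariate, its own coefficient absorbs the Y0/k term. The treatment estimate and its standard error then shrink by the same factor, so t and p do not change. If Y0 is averaged in without being a covariate, the standard error does not shrink to match. At ρ = 0.6 the per-infant variance is 0.6 + 0.4/5 = 0.68 for five days and 0.6 + 0.4/4 = 0.70 for the four post-entry days, so power is lost.

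**6. The alternative.** At ρ = 0.6, a model on all available post-entry scores with the entry score as covariate kept the simulated bias at 0.03 SD or less and rejection near 5%. At equal 30% mortality, power for a 0.6 SD effect rose from about 42–48% to 87–89%. Most of that gain comes from the entry score. Adjustment cuts the per-infant variance to 0.70 − 0.6² = 0.34. With 29.4/2 = 14.7 per arm, the standard error falls from √(2 × 0.68/14.7) = 0.304 to √(2 × 0.34/14.7) = 0.215. Keeping all 21 per arm takes it to √(2 × 0.34/21) = 0.180 at best.

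**The case against.** Several points on the other side stand.

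- **No complete-case rule is written.** Dropping infants is a property of the classical method, and software may keep partial series. Averaging all available rows cut the bias at g = 0.7 to about 0.05 SD (30% v 15%) or 0.07 SD (30% v 10%), and to about zero when day of death was spread evenly over days 2 to 5. The gap in the text remains, but its effect depends on how the method is run.
- **The upper figures are near worst case.** The 30% covers the neonatal period, and section 2 says up to 30% and that cooling reduces mortality. Adjusting for the entry score, which the plan permits, cut the bias under the most extreme assumptions from 0.17 to 0.10 SD.
- **Survival is watched.** Section 11 gives the safety committee survival by coded arm every six months, so a survival harm would not rest on this score alone to be seen.
- **The score is minor.** Section 2 makes seizures primary and lists injury markers, an EEG composite and development as secondary. No sample size rests on the score.

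A reader might infer that the entry score is both outcome and covariate. The documents do not say so: covariates are conditional, and nothing places the entry value in the outcome series. A reader might also infer that milder infants leave the series through early discharge. No section supports that, and 72 h of cooling, 12 h of rewarming, five daily doses and MRI on day 5–7 make it unlikely within about five days.

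**Conclusion.** The point holds as a gap in specification with a modest possible bias. The plan fixes neither the scoring days nor the handling of deaths, and the method it names is poorly suited to a series that death can cut short. At 30% v 15% mortality the spurious difference is about 0.03 to 0.06 SD with half the deaths in the scored period and 0.09 to 0.18 SD with all of them. It is opposite in sign to the survival effect, and zero if mortality is equal or unrelated to severity. The range rests on the assumed mortality difference, timing of deaths and link to severity, none of which the documents give. The loss of precision does not need a mortality difference: standard errors are 8% to 20% wider at 30% mortality.

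The role of the entry score is undetermined. If it is averaged in, the estimate shrinks to 75–80% for four to five days; if it is also a covariate, the test result is unchanged. Priority is low to moderate.

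**What to change.** Replace the sentence in section 9 with wording such as: *Scores on fixed post-entry days covering cooling and rewarming will be analysed by a linear mixed model using every available score, with treatment, day and treatment-by-day. The entry score is a covariate only and is not an outcome. Deaths by arm are shown beside the scores. A supportive rank analysis gives infants who have died the worst rank from the day of death.* The scoring days should be listed by number.

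The cost is a few sentences of analysis text and one extra supportive analysis on data already collected. The mixed model assumes that scores are missing at random, which death in the sicker infants may violate. The worst-rank analysis mixes death with severity, so it is supportive only.
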